6.3 Specific Recommendations for Management of Clinical Events

Adverse drug reactions such as thrombocytopenia, diarrhea, fatigue, nausea, vomiting, and rash have been associated with MLN9708 treatment. Management guidelines regarding these events are outlined below. Further details of management of MLN9708 AEs are described in Section 6 of the MLN9708 IB.

6.3.1 Prophylaxis against Risk of Infection

Antiviral therapy such as acyclovir or valacyclovir may be initiated as clinically indicated and per institutional standards. Other antivirals are also acceptable. Patients who do not receive antiviral therapy should be made aware of risks, such as reactivation of herpes zoster and herpes simplex viruses.

6.3.2 Nausea and/or Vomiting

Standard anti-emetics including 5-hydroxytryptamine 3 serotonin receptor antagonists are recommended for emesis if it occurs once treatment is initiated based on the patient's susceptibility to nausea and vomiting; prophylactic anti-emetics may also be considered at the discretion of the investigator. Fluid deficit should be corrected before initiation of study drug and during treatment.

6.3.3 Diarrhea

Prophylactic antidiarrheals will not be used in this protocol. However, diarrhea should be managed according to clinical practice, including the administration of antidiarrheals once infectious causes are excluded. Fluid intake should be maintained to avoid dehydration. Fluid deficit should be corrected before initiation of treatment and during treatment.

CONFIDENTIAL

STUDY DRUG: MLN9708
FINAL PROTOCOL: 11 APRIL 2014
AMENDMENT NUMBER 3: 11 FEBRUARY 2016

SCRI INNOVATIONS STUDY NUMBER: MM 42

VERSION 4

6.3.4 Erythematous Rash With or Without Pruritus

Rash has been reported with MLN9708. As with bortezomib, rash with or without pruritus has been reported with MLN9708, primarily at the higher doses tested. The rash may range from some erythematous areas, macular and/or small papular bumps that may or may not be pruritic over a few areas of the body, to a more generalized eruption that is predominately on the trunk or extremities. Rash has been most commonly characterized as maculopapular or macular. To date, when it does occur, rash is most commonly reported within the first 3 cycles of therapy. The rash is often transient, self-limiting, and is typically Grade 1 to 2 in severity.

Symptomatic measures such as antihistamines or corticosteroids (oral or topical) have been successfully used to manage rash and have been used prophylactically in subsequent cycles. The use of a topical, IV, or oral steroid (10mg of prednisone/day) is permitted. Management of a Grade 3 rash may require intravenous antihistamines or corticosteroids. Administration of MLN9708 (and/or other causative agent if given in combination) should be modified per protocol and re-initiated at a reduced level from where rash was noted (also, per protocol).

In line with clinical practice, dermatology consult and biopsy of Grade 3 or higher rash or any SAE involving rash is recommended. Prophylactic measures should also be considered if a patient has previously developed a rash (eg, using a thick, alcohol-free emollient cream on dry areas of the body or oral or topical antihistamines). . In the event of rash, a skin biopsy is suggested to assess etiology.

A rare risk is Stevens-Johnson syndrome, a severe, life-threatening or deadly rash with skin peeling and mouth sores, which should be managed symptomatically according to standard medical practice. In the case of rash, punch biopsies for histopathological analysis are encouraged at the discretion of the Investigator.

6.3.5 Thrombocytopenia

Thrombocytopenia has been reported with MLN9708. Blood counts should be monitored regularly as outlined in the protocol with additional testing obtained according to standard clinical practice. Thrombocytopenia may be severe but has been manageable with platelet transfusions according to standard clinical practice. MLN9708 administration should be modified as noted as per dose modification recommendations in the protocol when thrombocytopenia occurs (see Table 4). Therapy can be reinitiated at a reduced level upon recovery of platelet counts. A rare risk is thrombotic thrombocytopenic purpura, a rare blood disorder where blood clots form in small blood vessels throughout the body characterized by thrombocytopenia, petechiae, fever, or possibly more serious signs and symptoms. Thrombotic thrombocytopenic purpura should be managed symptomatically according to standard medical practice.

6.3.6 Neutropenia

Neutropenia has been reported with MLN9708. Blood counts should be monitored regularly as outlined in the protocol with additional testing obtained according to standard clinical practice. Neutropenia may be severe but has been manageable with G-CSF according to standard clinical practice. MLN9708 administration should be modified as noted as per dose modification

CONFIDENTIAL

STUDY DRUG: MLN9708
FINAL PROTOCOL: 11 APRIL 2014
AMENDMENT NUMBER 3: 11 FEBRUARY 2016

SCRI INNOVATIONS STUDY NUMBER: MM 42

VERSION 4

recommendations in the protocol when neutropenia occurs (see Table 4). Therapy can be reinitiated at a reduced level upon recovery of ANCs.

6.3.7 Fluid Deficit

Dehydration should be avoided since MLN9708 may cause vomiting, diarrhea, and dehydration. Acute renal failure has been reported in patients treated with MLN9708, commonly in the setting of the previously noted gastrointestinal toxicities and dehydration.. Fluid deficit should be corrected before initiation of study drug and during treatment.

6.3.8 Hypotension

Symptomatic hypotension and orthostatic hypotension have been reported with MLN9708. Blood pressure should be closely monitored while the patient is on study treatment and fluid deficit should be corrected as needed, especially in the setting of concomitant symptoms such as nausea, vomiting, diarrhea, or anorexia. Patients taking medications and/or diuretics to manage their blood pressure (for either hypotension or hypertension) should be managed according to standard clinical practice, including considerations for dose adjustments of their concomitant medications during the course of the study. Fluid deficit should be corrected before initiation of study drug and during treatment to avoid dehydration.

6.3.9 Posterior Reversible Encephalopathy Syndrome

One case of posterior reversible encephalopathy syndrome, which ultimately resolved, has been reported with MLN9708. This condition is characterized by headache, seizures and visual loss, as well as abrupt increase in blood pressure. Diagnosis may be confirmed by magnetic resonance imaging (MRI). If the syndrome is diagnosed or suspected, symptom-directed treatment should be maintained until the condition is reversed by control of hypertension or other instigating factors.

6.3.10 Transverse Myelitis

Transverse myelitis has also been reported with MLN9708. It is not known if MLN9708 causes transverse myelitis; however, because it happened to a patient receiving MLN9708, the possibility that MLN9708 may have contributed to transverse myelitis cannot be excluded.

7. STUDY ASSESSMENTS AND EVALUATIONS

7.1 Overview

All patients should visit the study center on the days specified within this protocol. The complete Schedule of Assessments for this study is shown in Appendix D.

Informed consent must be obtained ≤ 28 days prior to initiation of treatment and before any protocol-specific procedures are performed. The Baseline visit physical examination including vital signs, medical history, ECOG performance status, complete blood counts (CBC), differential and platelets, comprehensive metabolic profile (CMP), urinalysis, and PT/aPTT/INR should be done ≤ 7 days prior to initiation of treatment. However, if these initial examinations are obtained within 72 hours of first study drug administration they do not have to be repeated on

CONFIDENTIAL

STUDY DRUG: MLN9708
FINAL PROTOCOL: 11 APRIL 2014
AMENDMENT NUMBER 3: 11 FEBRUARY 2016

SCRI INNOVATIONS STUDY NUMBER: MM 42

VERSION 4

Day 1 of Cycle 1. A pregnancy test must be performed within 72 hours of first study drug administration.

7.2 Baseline Study Assessments

The following information will be collected and procedures will be performed for each patient at Baseline ≤ 7 days prior to initiation of treatment unless otherwise noted:

- Written informed consent prior to any other study-related procedures (≤ 28 days of first study drug treatment)
- Medical history including:
 - Review of systems
 - Prior treatments for all significant conditions, including neuropathy
 - ECOG performance status prior to conditioning for allogeneic transplant
 - Pre allogeneic transplant overall comorbidity index
 - Transplant history including
 - Conditioning regimens including total dose and start and end dates
 - Type of transplant (syngeneic, autologous or allogeneic; bone marrow versus peripheral blood stem cells; match related versus matched unrelated)
 - Date of transplant
 - Date of engraftment of white cells and platelets
 - Number of allogeneic CD34+ cells received (record for allogeneic transplant only)
 - Graft versus host disease prophylaxis
 - Post-transplant infections
 - Prior systemic therapy for multiple myeloma with start and end dates and best overall response to therapy
 - Prior radiation therapy for multiple myeloma with total dose, start and end dates
 - Prior surgeries for multiple myeloma and date
- Physical examination, including a neurological evaluation, measurements of height (first visit), weight, and vital signs (resting heart rate, blood pressure [BP], respiratory rate, and oral temperature)
- ECOG performance status (see Appendix A)
- Acute GVHD assessment with overall grade (see Appendix F)
- Chronic GVHD assessment with overall grade (see Appendix F)
- 12-lead ECGs in triplicate approximately 5 minutes apart

CONFIDENTIAL

STUDY DRUG: MLN9708

SCRI INNOVATIONS STUDY NUMBER: MM 42

FINAL PROTOCOL: 11 APRIL 2014

AMENDMENT NUMBER 3: 11 FEBRUARY 2016

VERSION 4

- Chest X-ray
- Concomitant medication review of all medications taken within 21 days of first planned study drug administration for conditions other than GVHD
- Concomitant medication review specifically for GVHD prophylaxis since receiving the allogeneic transplant
- CBC, including 3-part differential (total neutrophil count including bands, lymphocytes, monocytes) hemoglobin, hematocrit, and platelets
- CMP to include: glucose, blood urea nitrogen (BUN), creatinine (creatinine clearance calculated by Cockcroft-Gault), sodium, potassium, chloride, calcium, phosphorus, magnesium, carbon dioxide (CO₂), ALT, AST, ALP, lactate dehydrogenase (LDH), uric acid, total bilirubin, total protein, and albumin
- Urinalysis (dipstick)
- Coagulation tests: prothrombin time (PT), activated partial thromboplastin time (aPTT), and International Normalized Ratio (INR)
- Serum or urine pregnancy test for women of childbearing status (must be performed within 72 hours prior to the initiation of treatment)
- Disease assessments:
 - Bone marrow aspirate and biopsy including:
 - Quantify percent myeloma cell involvement
 - Obtain bone marrow aspirate for cytogenetics [i.e., diploidy, del(13)] and include number of metaphases analyzed
 - Mutations detected in fluorescent in situ hybridization (FISH) studies [i.e., t(4:14); t(11:14); del(17p)]
 - If available, provide MRD by flow cytometry
 - Skeletal survey (lateral radiograph of the skull, anteroposterior and lateral views of the spine, and anteroposterior views of the pelvis, ribs, femora, and humeri) ≤28 days of first study drug treatment.
 - Serum free light chains (SFLC)
 - Serum protein electrophoresis (SPEP) and serum protein immunofixation to determine M-protein
 - Urine protein electrophoresis (UPEP), urine protein immunofixation (requires a 24-hour urine collection), and total protein in urine
 - Serum quantitative immunoglobulins
 - Serum β₂ microglobulin

- Known plasmacytomas, utilize same modality used to assess original disease (i.e., PET, MRI, CT, etc)
- Gene expression profile analysis, if available (prior to bone marrow transplant and prior to enrolment)

7.3 Study Treatment Assessments

7.3.1 All Cycles Day 1 (± 2 days)

- Medical history update
- Physical examination including a neurological evaluation, measurement of weight, and vital signs
- ECOG performance status
- Acute GVHD assessment with overall score
- Chronic GVHD assessment with overall score
- AE assessment
- Concomitant medication review of all medications taken for conditions other than GVHD
- Concomitant medication review specifically for GVHD prophylaxis since receiving the allogeneic transplant
- Percentage chimerism conducted per institutional guidelines
- CBC including 3-part differential (total neutrophil count including bands, lymphocytes, monocytes) hemoglobin, hematocrit, and platelets
- CMP to include: glucose, BUN, creatinine (creatinine clearance calculated by Cockcroft-Gault), sodium, potassium, chloride, calcium, phosphorus, magnesium, CO₂, ALT, AST, ALP, LDH, uric acid, total bilirubin, total protein, and albumin
- Urinalysis (dipstick; if abnormal microscopic performed as clinically indicated)
- PT/aPTT/INR
- Biomarker blood sample collection for flow cytometry (conducted and reported by participating sites) and cytokine analysis (conducted by a central laboratory) (**Cycles 1 and 2 only for patients participating in the exploratory biomarker research**)

7.3.2 Cycle 1 Days 4, 8, and 15

- Physical examination (symptom directed) (**Days 8 and 15 only**)
- AE assessment (**Days 4, 8, and 15**)
- Concomitant medication review of all medications taken for conditions other than GVHD (**Days 4, 8 and 15**)
- Concomitant medication review specifically for GVHD prophylaxis since receiving the allogeneic transplant (**Days 4, 8 and 15**)

- Acute GVHD assessment with overall score, only for patients who have onset of GVHD post allogeneic transplant (**Days 8 and 15 only**)
- Chronic GVHD assessment with overall score, only for patients who have onset of GVHD post allogeneic transplant (**Days 8 and 15 only**)
- CBC, including 3-part differential (total neutrophil count including bands, lymphocytes, monocytes) hemoglobin, hematocrit, and platelets (**Days 8 and 15 only**)
- CMP to include: glucose, BUN, creatinine (creatinine clearance calculated by Cockcroft-Gault), sodium, potassium, chloride, calcium, phosphorus, magnesium, CO₂, ALT, AST, ALP, LDH, uric acid, total bilirubin, total protein, and albumin (**Days 8 and 15 only**)
- Urinalysis (dipstick; if abnormal microscopic performed as clinically indicated) (**Days 8 and 15 only**)
- Biomarker blood sample collection for flow cytometry (conducted and reported by participating sites) and cytokine analysis (conducted by a central laboratory) (**Days 4, 8 and 15 for patients participating in the exploratory research**)

7.3.3 Cycles 2 through 6 Days 8 and 15

- AE assessment
- Concomitant medication review of all medications taken for conditions other than GVHD
- Concomitant medication review specifically for GVHD prophylaxis since receiving the allogeneic transplant
- Acute GVHD assessment with overall score, only for patients who have onset of GVHD post allogeneic transplant
- Chronic GVHD assessment with overall score, only for patients who have onset of GVHD post allogeneic transplant
- CBC, including 3-part differential (total neutrophil count including bands, lymphocytes, monocytes) hemoglobin, hematocrit, and platelets

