6. DOSE MODIFICATIONS

If toxicity occurs, the toxicity will be graded utilizing the NCI CTCAE v4.0, and appropriate supportive care treatment will be administered to decrease the signs and symptoms thereof. Dose adjustments will be based on the organ system exhibiting the greatest degree of toxicity.

Study drug will be delayed if patients develop > Grade 2 GVHD and until GVHD is \leq Grade 2. If GVHD severity returns to \leq Grade 2, study drug can be restarted at the initial dose. If GVHD recurs, hold dose until GVHD is \leq Grade 2 and restart at next lower dose level. GVHD stopping criteria during administration of study drug includes the development of Grade 3 or 4 GVHD in more 80%, 70%, or 60% of the first 10, 20, or 30 patients enrolled, respectively. Patients that do not complete one cycle of maintenance because of GVHD will be replaced. Criteria for GVHD are presented in Appendix F.

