- ^c Physical examinations will include measurements of weight and vital signs (resting heart rate, blood pressure, respiratory rate, oral temperature). At the Baseline visit only, height will also be recorded. Physical examinations will be done on Day 1 of each cycle. In addition during Cycle 1 only, patients will have a symptom directed physical examination done on Days 4, 8, and 15.
- ^d Acute and chronic GVHD assessment is to be conducted at baseline and Day 1 of every cycle. Patients that develop GVHD will have the assessment conducted every visit on Days 1, 8, and 15 of every cycle.
- ^e Three 12-lead ECGs will be collected approximately 5 minutes apart at the Baseline visit. Additional ECGs will be done as clinically indicated.
- ^f Patients will be re-evaluated for response to treatment after 2 cycles of treatment. Response will be assessed at 8-week intervals (± 1 week) during study treatment. Patients with progressive disease (PD) or unacceptable toxicity should be discontinued from the study; patients with stable disease (SD) or response to therapy will continue treatment.
- ^g Hematology parameters include the following laboratory tests: CBC with 3-part differential (total neutrophil count including bands, lymphocytes, monocytes) hemoglobin, hematocrit and platelets.
- ^h CMP to include: glucose, BUN, creatinine (creatinine clearance calculated by Cockcroft-Gault), sodium, potassium, chloride, calcium, phosphorus, magnesium, CO₂, ALT, AST, ALP, LDH, uric acid, total bilirubin, total protein, and albumin.
- ⁱ A urine dipstick will be done weekly during Cycle 1. Thereafter, urine dipstick will be done on Day 1 of each 4-week cycle. If abnormalities are present on urine dipstick, additional testing (e.g., microscopic examination, urine protein:creatinine ratio [UPC], etc.) should be done as clinically indicated.
- ^j A serum pregnancy test will be performed only for women of childbearing potential within 72 hours of study drug administration (see Appendix C).
- ^k Biomarker blood samples: peripheral blood samples will be collected on Days 1 (pre-dose), 4, 8, and 15 of Cycle 1 and on Day 1 (pre-dose) of Cycle 2 only. Participating patients will include 3 patients at each dose level and 5 additional patients at the MTD/MPD.
- ^l Report percentage chimerism conducted by institutional guidelines. Above provided schedule is preferred, but not required.

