I	Maculopapular rash < 25% of body surface area without associated symptoms	Bilirubin from 2 mg/dl to < 3 mg/dl or 35-50 µmol/l	Diarrhea > 500-1000 ml/day; nausea and emesis
II	Maculopapular rash or erythema with puritis or other associated symptoms ≥ 25% of body surface area or localized desquamation	Bilirubin from 3 mg/dl to < 6 mg/dl or 51-102 µmol/l	Diarrhea > 1000 to 1500 ml/day; nausea and emesis
III	Generalized erythroderma or symptomatic macular, papular, or vesicular eruption with bullous formation or desquamation covering ≥ 50% of body surface area	Bilirubin 6 mg/dl to < 15 mg/dl or 103-225 µmol/l	Diarrhea > 1500 ml/day; nausea and emesis
IV	Generalized exfoliative dermatitis or bullous eruption	Bilirubin > 15 mg/dl or > 225 µmol/l	Diarrhea > 1500 ml/day; nausea and emesis. Abdominal pain or ileus

Overall Clinical Grading of Acute GVHD

Grade	Skin	Liver	GI tract	Performance status
0	0	0	0	0
I	1-2	0	0	0
II	1-3	1	1	1
III	2-3	2-3	2-3	2
IV	2-4	2-4	2-4	2-4

Reference for both tables for acute GVHD: Przepiorka et al. 1995

CONFIDENTIAL

STUDY DRUG: MLN9708

SCRI INNOVATIONS STUDY NUMBER: MM 42

FINAL PROTOCOL: 11 APRIL 2014

AMENDMENT NUMBER 3: 11 FEBRUARY 2016

VERSION 4

Organ Staging of Chronic GVHD

	SCORE 0	SCORE 1	SCORE 2	SCORE 3
PERFORMANCE SCORE:  KPS ECOG LPS	 Asymptomatic and fully active (ECOG 0; KPS or LPS 100%)	 Symptomatic, fully ambulatory, restricted only in physically strenuous activity (ECOG 1, KPS or LPS 80-90%)	 Symptomatic, ambulatory, capable of self-care, >50% of waking hours out of bed (ECOG 2, KPS or LPS 60-70%)	 Symptomatic, limited self-care, >50% of waking hours in bed (ECOG 3-4, KPS or LPS <60%)

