GI TRACT	 No symptoms	 Symptoms such as dysphagia, anorexia, nausea, vomiting, abdominal pain or diarrhea without significant weight loss (<5%)	 Symptoms associated with mild to moderate weight loss (5-15%)	 Symptoms associated with significant weight loss >15%, requires nutritional supplement for most calorie needs OR esophageal dilation
LIVER	 Normal LFT	 Elevated Bilirubin, AP*, AST or ALT <2 x ULN	 Bilirubin >3 mg/dl or Bilirubin, enzymes 2-5 x ULN	 Bilirubin or enzymes > 5 x ULN

CONFIDENTIAL

SCRI INNOVATIONS STUDY NUMBER: MM 42

STUDY DRUG: MLN9708
 FINAL PROTOCOL: 11 APRIL 2014
 AMENDMENT NUMBER 3: 11 FEBRUARY 2016

VERSION 4

	SCORE 0	SCORE 1	SCORE 2	SCORE 3
LUNGS [†]	 No symptoms	 Mild symptoms (shortness of breath after climbing one flight of steps)	 Moderate symptoms (shortness of breath after walking on flat ground)	 Severe symptoms (shortness of breath at rest; requiring O ₂)
FEV1 				
DLCO 	 FEV1 > 80% OR LFS=2	 FEV1 60-79% OR LFS 3-5	 FEV1 40-59% OR LFS 6-9	 FEV1 ≤39% OR LFS 10-12
JOINTS AND FASCIA	 No symptoms	 Mild tightness of arms or legs, normal or mild decreased range of motion (ROM) AND not affecting ADL	 Tightness of arms or legs OR joint contractures, erythema thought due to fasciitis, moderate decrease ROM AND mild to moderate limitation of ADL	 Contractures WITH significant decrease of ROM AND significant limitation of ADL (unable to tie shoes, button shirts, dress self etc.)
GENITAL TRACT	 No symptoms	 Symptomatic with mild signs on exam AND no effect on coitus and minimal discomfort with gynecologic exam	 Symptomatic with moderate signs on exam AND with mild dyspareunia or discomfort with gynecologic exam	 Symptomatic WITH advanced signs (stricture, labial agglutination or severe ulceration) AND severe pain with coitus or inability to insert vaginal speculum

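### In Cycles 2-6, patients with GVHD are scored on Days 8 and 15 with no bilirubin scheduled, so liver worsening that should trigger the dose hold could be missed for up to two doses

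*Protocol*

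**What the plan says.** **Scores required.** Protocol Section 7.3.3 lists, for Days 8 and 15 of Cycles 2-6, an "Acute GVHD assessment with overall score, only for patients who have onset of GVHD post allogeneic transplant", together with the matching chronic GVHD item. Appendix D, note d, says the same: "Patients that develop GVHD will have the assessment conducted every visit on Days 1, 8, and 15 of every cycle".

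**Blood tests scheduled.** On those days Section 7.3.3 lists a CBC and no other blood test. In Appendix D the CBC row is marked and the chemistry panel (CMP) row is empty. Bilirubin, ALT, AST and ALP are part of the CMP. In Cycles 2-6 the CMP is scheduled on Day 1 only (Section 7.3.1). In Cycle 1, Section 7.3.2 schedules it on Days 8 and 15 alongside the same GVHD scores.

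**What the scores need.** The acute organ staging table in Appendix F defines liver stage by bilirubin only; stage II, for example, is "Bilirubin from 3 mg/dl to < 6 mg/dl". The chronic table scores the liver on bilirubin and enzymes; score 1 reads "Elevated Bilirubin, AP*, AST or ALT <2 x ULN". In the table headed "Overall Clinical Grading of Acute GVHD", Grade II lists liver stage 1, Grade III lists stages 2-3 and Grade IV lists stages 2-4.

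**How the grade is used.** Section 6 states: "Study drug will be delayed if patients develop > Grade 2 GVHD". The same section uses the grade for study-level monitoring: "GVHD stopping criteria during administration of study drug includes the development of Grade 3 or 4 GVHD".

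**The concern.** The protocol asks for an overall acute GVHD score on days when a dose is due, but does not schedule the one laboratory value that determines its liver component. Bilirubin decides whether the liver component alone falls on the Grade II side or the Grade III side of the hold line. If sites follow the schedule as written, the liver part of a Day 8 or Day 15 score can draw only on the previous Day 1 result.

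The patients concerned are eligible by design. They enter 45 to 120 days after transplant, and Section 3.2 admits Grade 1 or 2 GVHD if it needs no more than 0.5 mg/kg methylprednisolone or equivalent. At stake is the safety of individual patients: a hold that Section 6 intends might not be triggered until the next cycle.

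**Working it through.** This is a count from the visit schedule. The documents state no figure to reproduce.

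**Inputs**
- Dosing on Days 1, 8 and 15 of each 28-day cycle, for 6 cycles (Section 5).
- CMP on Day 1 of every cycle and on Cycle 1 Days 8 and 15 (Sections 7.3.1 and 7.3.2, Appendix D).
- GVHD score on Days 1, 8 and 15 of every cycle once GVHD has developed (Appendix D, note d).
- Day 1 visit window of 2 days either side (Section 7.3.1).

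**Dosing days without a scheduled bilirubin**
- Dosing days: 6 × 3 = 18.
- With a CMP: 6 + 2 = 8. A baseline CMP within 72 hours may stand in for Cycle 1 Day 1, which does not change the count.
- Without: 18 − 8 = 10, which is Days 8 and 15 of five cycles (5 × 2 = 10). 10/18 = 56%.

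Ten is a ceiling. For a patient who has GVHD from the start of Cycle k (k = 2 to 6) and completes treatment, the number is 2 × (7 − k): 10, 8, 6, 4 or 2.

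**Age of the last scheduled bilirubin**
- Day 8: 8 − 1 = 7 days. Day 15: 15 − 1 = 14 days.
- If Day 1 uses its window while Days 8 and 15 stay on the calendar: 7 ± 2 = 5 to 9 days, and 14 ± 2 = 12 to 16 days.

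**Doses exposed per episode**
- Liver worsening that begins after the Day 1 sample can pass the Day 8 and Day 15 doses: two doses.
- The next dose is Day 1 of the following cycle, where a CMP is scheduled.

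**Link to the hold rule, from Appendix F**

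| Bilirubin | Acute liver stage | Overall grades listing that stage | Above the Section 6 hold line? |
|---|---|---|---|
| 2 to < 3 mg/dl | 1 | II | No |
| 3 to < 6 mg/dl | 2 | III, IV | Yes |

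A rise across 3 mg/dl therefore moves the liver component over the hold line, and no other input to the acute liver stage can reveal it.

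**The case against.** **The investigator can order the test.** Section 5.1 calls for toxicity monitoring as needed, and nothing bars an unscheduled bilirubin. No text tells sites to carry the Day 1 value forward, so one may argue that requiring an overall score implies obtaining its inputs. Skin and gut can still be staged clinically that day. This stands as a limit: the gap is in what is scheduled, and careful sites may close it. It does not remove the point, because a required score that decides dosing should not depend on an optional test across up to five sites.

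**The schedule steps down on purpose.** Urinalysis and the symptom-directed examination also disappear from Days 8 and 15 after Cycle 1, the DLT window. Reducing routine chemistry for all patients is a reasonable economy. The documents give no reason to drop the liver input for the subgroup that must still be scored.

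Three stronger readings are tempting, but the documents do not support them.

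- *The gap undermines the GVHD stopping criteria.* Those require Grade 3-4 GVHD in more than 80%, 70% or 60% of the first 10, 20 or 30 patients, meaning at least 9, 15 or 19 patients. Every Day 1 has a CMP, so persistent liver worsening is picked up by the next cycle. Only a rise that resolves between Day 1 visits would escape, and nothing shows that this could change the tally.
- *The gap prolongs holds.* A hold starting on Day 15 loses no dose before the next Day 1 CMP. A hold starting on Day 8 could lose at most the Day 15 dose to the lag. A liver-driven hold begun within a cycle normally presupposes an unscheduled test, and the same route is open for release.
- *Missing enzymes also affect the hold.* Appendix F gives chronic organ scores of 0 to 3 with no table converting them to the grades that Section 6 uses. Only bilirubin is tied to the hold rule.

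**Conclusion.** The point holds as a gap in scheduled safety data for patients with GVHD. On Days 8 and 15 of Cycles 2-6, the acute score that Section 6 uses lacks its only liver input, and new liver worsening that should hold the drug could be missed for up to two doses per cycle. The extent is at most 10 of 18 dosing days per patient.

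This rests on three assumptions: sites do only the scheduled tests; the patient has GVHD by Cycle 2 and completes six cycles (fewer days otherwise); and the liver is the component that crosses the line, since skin or gut involvement could trigger the hold without bilirubin.

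The documents give no rate of GVHD or of liver involvement, so the number of patients affected is unknown. The counts are certain from the schedule; how often harm would follow is not. The change is worth making because it is specific and cheap.

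**What to change.** For patients with GVHD onset only, amend Section 7.3.3 and the Appendix D schedule to add total bilirubin to the CBC draw already taken on Days 8 and 15 of Cycles 2-6, with the result reviewed before that day's dose. ALT, AST and ALP may be run on the same sample to complete the chronic liver score, but the hold rule does not need them.

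For these patients, dosing days with a same-day scheduled bilirubin rise from 8 of 18 to as many as 18 of 18. The cost is at most 10 extra chemistry samples per affected patient (5 cycles × 2 days), with no new visit or draw, and a possible short wait for the result before dosing.
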